NCT02848599

ID: 25-1:6563-3/2014

Document Date: May 26, 2017

The Influence of  
Postoperative Analgesia  
on Systemic Inflammatory  
Response and POCD  
After Femoral Fractures  
Surgery

The study was approved by the University Hospital Osijek Ethics Committee (Approval number 25-1:6563-3/2014, 19.5.2014.) and written informed consent was obtained from all subjects. The study design was a prospective, randomized, controlled trial. All patients received spinal anesthesia and one of two techniques of postoperative analgesia: intravenous patient-controlled analgesia (PCA) with morphine or patient-controlled epidural analgesia (PCEA) with 0.125% levobupivacaine. According to technique of postoperative analgesia which was applied, patients were allocated into two groups, the morphine group and the levobupivacaine group. Randomization was done before surgery by pulling out the envelope in which it was written the group division. Inclusion criteria were age  $\geq$  65, American Society of Anesthesiologists (ASA) physical status I-III, Mini-Mental State Examination (MMSE) score  $\geq$  17. Exclusion criteria were age  $<$  65, ASA physical status > III, MMSE score  $<$  17, history of dementia, schizophrenia, Parkinson's disease and cerebrovascular disease, use of opioids and benzodiazepines longer than one month before surgery, alcoholism, severe liver disease (class C according to Child-Pugh classification), severe kidney disease requiring hemodialysis, multiple trauma and the presence of head injury, communication issues such as serious hearing or visual impairment, any contraindication for regional anesthesia and for the both techniques of postoperative analgesia. Cefazolin 1g was given to all patients 30 minutes before incision and two other doses were given postoperatively. All patients were sedated with midazolam, 2 to 3 mg intravenously, before induction of anesthesia. In the morphine group spinal anesthesia was induced with subarachnoidally injection of 12.5-15 mg 0.5% levobupivacaine. In the levobupivacaine group combined spinal-epidural anesthesia was performed. First, the epidural space was entered with Tuohy epidural needle and the spinal needle was introduced via the lumen of the epidural needle into the subarachnoid space through which 12.5-15 mg of 0.5% levobupivacaine was injected. After that epidural catheter was inserted in the epidural space and its position was checked radiologically and confirmed with the test dose of 0.5% levobupivacaine after the spinal anesthesia was released. During the operation blood pressure was measured non-invasively every 5 minutes and its decrease greater than 20% from preoperative values was corrected by fluid administration and incremental IV injections of vasoconstrictors. The ECG and peripheral oxygen saturation by pulse oximeter were continuously monitored. Postoperative analgesia was obtained using patient-controlled analgesia (PCA) for the first 72 h. In the morphine group intravenous PCA was provided with the following settings: 0.5-2 mg/h basal flow, 0.5 mg bolus dose, and a 20-min lockout. Postoperative epidural PCA analgesia was obtained with 0.125% levobupivacaine with 6-12 ml/h basal flow, 2 ml bolus dose, and a 20-min lockout. Analgesia was assessed by Numerical Rating Scale (NRS), from 0 (no pain) to 10 (maximum pain) every three hours 72h postoperatively and then 3 times a day until discharge. In all patients complete blood count, differential blood count, CRP and fibrinogen were calculated 30 min before induction of anesthesia, 24h, 72h and 120h postoperatively. Blood glucose level was measured every 4 hours for 72h after

surgery and further depending on the values. The plasma concentrations of IL-6 was measured 30 min before induction of anesthesia, 24h and 72h postoperatively. Duration of surgery, blood loss, erythrocyte transfusion, body temperature and postoperative hospital stay were recorded. Cognitive functions were assessed using Mini-Mental State Examination (MMSE) preoperatively (baseline) and from the 1st to the 5th postoperative day and on the day of discharge (the day of surgery was marked as 0 day), once a day between 6 and 8 am. Anxiety and depression were assessed using Hospital Anxiety and Depression Scale (HADS) preoperatively (baseline) and on the 1st and 5th postoperative day and on the day of discharge once a day, at the same time when cognitive functions were evaluated.

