NCT02848599

ID: 25-1:6563-3/2014

The Influence of
Postoperative Analgesia
on Systemic Inflammatory
Response and POCD
After Femoral Fractures
Surgery

Document Date: May 26, 2017

Category data were represented by absolute and relative frequencies. Variations of category variables were tested by Fisher's exact test. The numerical data are described by the median and the limits of the interquartile range. The normality of distribution of observed numeric variables was tested by the Shapiro -Wilk test. The differences between the normal distribution of numeric variables between the two independent groups were tested by Mann-Whitney's In Test. To determine the difference between the two dependent samples, Friedman's test was used. Logistic regression was used to assess the influence of several factors on the likelihood that POCD would develop in the observed subjects. The receiver operating curve (ROC) analysis was used to determine the optimal threshold, area under the curve (AUC), specificity, and sensitivity of the tested parameters. All P values were two-tailed. The level of significance was set at Alpha = 0.05. The statistical analysis was performed using MedCalc Statistical Software version 14.12.0 (MedCalc Software bvba, Ostend, Belgium; <http://www.medcalc.org>; 2014)

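### Does the protocol group patients by the analgesia they received and not by the envelope they drew?

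*Protocol*

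**What the plan says.** The protocol is one continuous narrative without section headings. On design it says "The study design was a prospective, randomized, controlled trial". On group membership it gives two consecutive statements: "According to technique of postoperative analgesia which was applied, patients were allocated into two groups, the morphine group and the levobupivacaine group", and then "Randomization was done before surgery by pulling out the envelope in which it was written the group division".

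It next describes the anaesthetic by group: the morphine group has a spinal alone, while "In the levobupivacaine group combined spinal-epidural anesthesia was performed". For the epidural catheter it adds that "its position was checked radiologically and confirmed with the test dose of 0.5% levobupivacaine after the spinal anesthesia was released".

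The SAP, also a single narrative, gives the between-group tests. For numerical variables: "The differences between the normal distribution of numeric variables between the two independent groups were tested by Mann-Whitney's In Test". For categorical variables: "Variations of category variables were tested by Fisher's exact test". Neither document uses the terms intention-to-treat, per-protocol or as-treated, and neither says in which group a patient is analysed if the assigned technique fails or is changed.

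**The concern.** Two sentences in a row seem to define the groups differently, one by the technique applied and one by the envelope. The definitions coincide unless a patient does not receive the assigned technique, and the protocol contains a step where that could happen in one arm only. The epidural catheter is checked and tested after randomisation, and the morphine arm has no matching step.

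If patients with failed catheters were counted as morphine, or dropped, and if failure were related to cognitive or inflammatory prognosis, the arms would no longer be comparable. The Mann-Whitney and Fisher tests could then reject too often with no true effect. Because the SAP names no analysis population, nothing in it rules this out explicitly.

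**Working it through.** **Reading the text**

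1. The design sentence says the trial is randomised. The verb in the disputed sentence is one of allocation, and the sentence directly after it says how allocation was done: by an envelope, before surgery, with the group written inside.
2. The group then determines the anaesthetic: spinal alone in one, combined spinal-epidural in the other. This happens before any postoperative analgesia has been given. A group defined only by the analgesia later applied could not decide the earlier anaesthetic, but a group fixed by the envelope could.
3. So the disputed sentence most plausibly explains why the groups are called morphine and levobupivacaine. It is loosely worded, but it does not set an as-treated rule.
4. The SAP's two independent groups are then the protocol's two randomised groups. The SAP offers no other definition.
5. The catheter step is described as a check and a confirmation. No failure, conversion or crossover is reported. Patients with contraindications to regional anaesthesia or to the analgesia techniques are excluded, which removes one foreseeable reason for changing technique.

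**How large could it be?**

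The plan gives no figure to reproduce: no sample size, SD or failure rate is stated. Only the two-sided 5% level comes from the SAP. Everything else is assumed:

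- n = 40 per arm
- f = share of the epidural arm that fails: 5%, 10%, 20%
- d = prognosis of failures minus non-failures, in SD units: 0, 0.2, 0.5, 1.0
- no true treatment effect; SD fixed at 1

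With overall mean 0, non-failures have mean -fd and failures (1-f)d.

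- *Failures counted as morphine:* the levobupivacaine mean is -fd and the morphine mean is f(1-f)d/(1+f). The bias is 2fd/(1+f), with standard error √[1/(n(1-f)) + 1/(n(1+f))].
- *Failures left out:* the bias is fd, with standard error √[1/(n(1-f)) + 1/n].
- *Type I error:* Φ(-1.96 - bias/SE) + Φ(-1.96 + bias/SE).

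Worked example, f = 20%, d = 0.2, counted as morphine: bias = 2 × 0.2 × 0.2/1.2 = 0.067 SD; SE = √(1/32 + 1/48) = 0.228; ratio 0.29; type I error 6.0%.

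Type I error at f = 5%, 10%, 20%:

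| d | Counted as morphine | Left out |
|---|---|---|
| 0 | 5.0%, 5.0%, 5.0% | 5.0%, 5.0%, 5.0% |
| 0.2 | 5.1%, 5.3%, 6.0% | 5.0%, 5.1%, 5.3% |
| 0.5 | 5.5%, 6.9%, 11.3% | 5.1%, 5.5%, 7.1% |
| 1.0 | 7.1%, 12.8%, 30.9% | 5.6%, 7.2%, 13.5% |

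With 100 per arm and failures counted as morphine, d = 0.2 gives 5.2%, 5.8% and 7.5%. The extreme corner (f = 20%, d = 1.0) gives 64%, but by normal approximation only, with SD held at 1 although the enlarged morphine group would be a more variable mixture. At 40 per arm the same corner falls from 31% to about 25% when the SAP's Mann-Whitney test is simulated. Analysed by envelope, the simulated error was 4.4% to 5.8% in every scenario, which is 5% within or close to simulation error (4,000 trials per scenario).

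**The case for a change.** The strongest case for acting is that the SAP's silence stands whatever the disputed sentence means. No analysis set is named, the possible selection is one-sided, and one-sided selection after randomisation is what analysis as randomised guards against. A clarifying sentence and a count of technique changes per arm would cost little, and a count of zero would close the question.

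Much of this is correct. The omission is real, the arithmetic above is sound, and a stated analysis set would have been better reporting. What it does not show is that the plan leads to a wrong analysis. The plan contains only one operational assignment rule, the envelope, and an analyst who follows it gets a comparison that holds its level. The inflated figures need three things together: failures occurred, they were moved or dropped despite the randomisation, and failure was materially related to prognosis. The documents support none of the three. Technique changes are also not among the recorded items listed in the protocol, so a count might have to be retrieved from patient records.

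**Conclusion.** The concern does not call for a change. The phrase about the technique applied is loose wording, and the neighbouring sentences on randomisation and on the anaesthetic settle its meaning as the randomised groups. The missing analysis population is a gap that an analyst fills in the ordinary way, by analysing patients in the group their envelope assigned.

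The effect on results cannot be quantified from the documents. It is zero if no patient changed technique, if patients were analysed by envelope, or if failure is unrelated to prognosis. At 40 per arm with an assumed prognostic difference of 0.2 SD, type I error would be at most 6.0%. The larger values depend on assumed differences of 0.5 to 1.0 SD and, for the most part, on failure rates of 10% to 20%. The conclusion rests on reading the protocol's narrative as a whole. It would need revisiting if trial records showed that patients had changed technique and been analysed by what they received.

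### IL-6, CRP and fibrinogen are measured before surgery but not used in the comparison between arms, so pre-existing inflammation and time since fracture cost avoidable precision

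*Protocol*

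**What the plan says.** **Measurement (Protocol).** On the blood markers: "CRP and fibrinogen were calculated 30 min before induction of anesthesia, 24h, 72h and 120h postoperatively". On IL-6: "The plasma concentrations of IL-6 was measured 30 min before induction of anesthesia, 24h and 72h postoperatively". Each of the three markers therefore has a value from before the surgery and before the analgesia under study.

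**Eligibility (Protocol).** Patients are included on age, ASA class and MMSE score. The only drug-use exclusion is "use of opioids and benzodiazepines longer than one month before surgery". The comorbidity and injury exclusions include "severe kidney disease requiring hemodialysis, multiple trauma and the presence of head injury". The list closes with "any contraindication for regional anesthesia and for the both techniques of postoperative analgesia". No item names infection, inflammatory disease, or steroid or immunosuppressant use, and no window from fracture to surgery is set.

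**Recorded variables (Protocol).** "Duration of surgery, blood loss, erythrocyte transfusion, body temperature and postoperative hospital stay were recorded". Time since fracture is not in this list.

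**Allocation (Protocol).** "Randomization was done before surgery by pulling out the envelope in which it was written the group division". No stratification is described.

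**Analysis (SAP).** Numeric variables are compared between the two groups by Mann-Whitney, two-sided at 0.05. Friedman's test is assigned to dependent samples. The only multivariable model is a logistic regression for POCD. No analysis of the markers between arms uses the preoperative value or any other covariate.

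**The concern.** Systemic inflammatory response comes first in the trial's title. Patients aged 65 or over with a femoral fracture arrive with inflammation that has nothing to do with the analgesia: the fracture itself, at an unrecorded interval before surgery, and in some patients infection, chronic disease or drugs that alter the response. All postoperative samples are timed from surgery, so two patients at the 24-hour sample may be at different distances from the injury.

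A Mann-Whitney test on the postoperative values treats all of this as random spread. Friedman's test may use the preoperative value to describe change over time, but it does not bring that value into the comparison between arms. The plan thus collects the most useful covariate for each marker and leaves it out. What is at stake is power and the width of the interval for the arm difference.

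**Working it through.** **Step 1: is there a figure to reproduce?** No. The documents state no sample size, SD, effect size or power. Alpha of 0.05, two-sided, comes from the SAP. Every other input below is an assumption.

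**Step 2: assumptions.** Log markers with SD 1 in unaffected patients; n = 40 per arm; true shift 0.65 SD; correlation ρ of 0.3 to 0.5 between the preoperative and postoperative log value; a share p of patients whose marker is d SD higher both before and after surgery.

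**Step 3: formulas.** The affected patients add v = p(1−p)d² to the variance.

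- Unadjusted variance: 1 + v
- Variance after adjusting for baseline: (1 + v) − (ρ + v)²/(1 + v)
- Power: Φ(0.65/√(2V/n) − 1.96)

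**Step 4: 10% of patients at +1.5 SD.** v = 0.1 × 0.9 × 2.25 = 0.2025.

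- No affected patients: V = 1, 0.65/0.2236 = 2.907, power 83%.
- Unadjusted, all patients: V = 1.2025, 0.65/0.2452 = 2.651, power 76%.
- Affected patients excluded, 36 per arm: V = 1, 0.65/0.2357 = 2.758, power 79%.
- Baseline-adjusted, all patients, ρ = 0.3: V = 1.2025 − 0.5025²/1.2025 = 0.9925, power 83%.
- Baseline-adjusted, all patients, ρ = 0.5: V = 1.2025 − 0.7025²/1.2025 = 0.7921, power 90%.

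These normal approximations run a few points high for Mann-Whitney. Simulation of the same cases, and of a heavier one, gave:

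| Affected | Mann-Whitney, all | Mann-Whitney after exclusion | ANCOVA, all (ρ 0.3 to 0.5) |
|---|---|---|---|
| 10% at +1.5 SD | 73% | 75-77% | 83-88% |
| 20% at +2 SD | 60-62% | 69-71% | 79-88% |

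Simulation error is about one to two points.

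**Step 5: where baseline adjustment does less well.**

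- *No residual correlation (ρ = 0), 10% at +1.5 SD.* V = 1.2025 − 0.2025²/1.2025 = 1.1684, power 77% by formula against 79% for exclusion. The two are roughly equal. At +2 SD exclusion is modestly better.
- *Condition changes only the later response and does not show at baseline.* The adjusted variance is then 1 + v − ρ². With 20% at +1.5 SD, v = 0.36. At ρ = 0.5, V = 1.11 and power is 79% keeping everyone, against 85% when they are dropped and the remaining 32 per arm are adjusted (V = 0.75). If the shift does show at baseline, keeping everyone gives V = 1.36 − 0.86²/1.36 = 0.8162 and 90%, against the same 85%.

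**Step 6: time since fracture.** If it explains a share R² of the variance, the variance is inflated by 1/(1 − R²). For an assumed R² of 5% to 20% this is 1.05 to 1.25. At 40 per arm, the 83% of step 4 falls to 81% (0.65/0.2294 = 2.833) or 74% (0.65/0.25 = 2.6). Baseline adjustment would recover part of this; the recorded interval is needed for the rest. The documents give no spread of delays, so R² cannot be narrowed.

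**The case against.** The strongest reply is that this is a preference about precision. Affected patients fall into both arms by chance, a false difference from chance imbalance is already covered by the 5% error rate, and broad eligibility is legitimate in a trial that also studies POCD. That stands, and it limits the point to lost power.

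A reader might go further and infer that the eligibility criteria are defective, and that infection, inflammatory disease and steroid use should have been excluded. The documents do not support this, for four reasons.

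- The contraindication clause and the ASA limit may already remove some patients with infection, though the protocol does not say so.
- At 10% affected and +1.5 SD, exclusion gains only about two to four points, and in the 20% case it gives up one patient in five.
- Under the stated correlations, with the shift present at baseline, adjusting for baseline does better and loses nobody.
- The protocol is written in the past tense and dated May 2017, so enrolment appears complete and new entry criteria could not be applied.

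One argument for exclusion survives. Steroids or immunosuppressants may alter the later response without showing in the preoperative value, and the last case in step 5 then favours leaving those patients out. That justifies a sensitivity analysis, not a change in who is analysed.

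Fracture time may also sit in the admission chart even though the protocol does not list it. That makes the fix easier, but the planned analysis still does not use it.

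**Conclusion.** The point holds as a matter of analysis and precision. The plan measures each marker before surgery and then compares arms without it, and nothing in the plan accounts for time since fracture. There is no bias.

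In the illustrated 10% case, baseline adjustment recovers roughly 10 to 15 points of power (73% to 83-88%), against 2 to 4 for exclusion. The gain rests on the assumed 40 per arm, 0.65 SD shift, correlation of 0.3 to 0.5, and a shift present before surgery. It shrinks towards that of exclusion if the correlation is near zero. The actual loss in this trial cannot be derived from the documents.

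**What to change.** 1. In the SAP, compare log-transformed IL-6 (24h, 72h), CRP and fibrinogen (24h, 72h, 120h) between arms at each time by ANCOVA on all randomised patients, adjusting for the log preoperative value of the same marker. Report the ratio of geometric means with its 95% interval.
2. Take hours from fracture to surgery from the admission record and add them as a second covariate. State how a missing value is handled, so that no patient is lost; filling it with the overall mean is enough for a covariate fixed before surgery.
3. Leave the eligibility criteria as they are. At most, report one sensitivity analysis of the markers that omits patients with charted infection, inflammatory disease, or steroid or immunosuppressant use, with the list fixed before it is run and the analysis labelled post hoc if data are already in hand.
4. If marker data have already been seen, say so when ANCOVA is added and report the planned Mann-Whitney result beside it.

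The cost is a paragraph in the SAP and a chart lookup for one time per patient, plus three chart items if the sensitivity analysis is done. No new samples are needed, and the POCD analysis is unaffected.

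### Fracture site and operation type are not named for eligibility, recording, allocation or analysis, which costs precision and leaves a chance imbalance in surgical trauma hard to interpret.

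*Protocol*

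**What the plan says.** The protocol is one unheaded text. Its parts that bear on this point are:

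- **Title:** the setting is surgery "After Femoral Fractures". No site or procedure is given.
- **Inclusion criteria:** age, "American Society of Anesthesiologists (ASA) physical status I-III" and MMSE. No fracture or operation is mentioned.
- **Exclusion criteria:** these include "multiple trauma and the presence of head injury", but nothing on the site of the femoral fracture or the procedure.
- **Allocation:** "Randomization was done before surgery by pulling out the envelope in which it was written the group division". No stratification is described.
- **Recorded surgical and perioperative items:** "Duration of surgery, blood loss, erythrocyte transfusion, body temperature and postoperative hospital stay were recorded".
- **Inflammation outcomes:** "The plasma concentrations of IL-6 was measured 30 min before induction of anesthesia, 24h and 72h postoperatively". CRP, fibrinogen and blood counts are taken before anaesthesia and at 24, 72 and 120 hours.

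The SAP compares numeric variables between the two groups with a Mann-Whitney test, which takes no covariate. Its only multivariable model is for POCD: "Logistic regression was used to assess the influence of several factors on the likelihood that POCD would develop in the observed subjects". The factors are not named.

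**The concern.** Femoral fracture surgery can include operations of different extent, and the extent of the operation can be expected to influence postoperative IL-6, CRP and fibrinogen. Operation class is normally settled before the envelope is drawn, so it could serve as a true baseline covariate. As written, the plan neither collects it nor uses it.

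Two things are lost. First, variation between operation types stays in the residual of the inflammation comparison and widens it. Second, if the arms happen to differ in their mix of operations, a reader cannot see this and cannot judge how much of an observed difference in markers might come from it.

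**Working it through.** **What the documents give.** They give a two-sided alpha of 0.05 and an unadjusted Mann-Whitney comparison. They state no sample size, power, effect size or case mix, so there is no figure of the plan's own to reproduce. The arm sizes, the split of operation types and the difference between types below are assumptions.

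**1. How often the arms differ by chance.** Assume equal arms of n, simple randomisation, and two operation types each making up half the patients. The number of one type in each arm is then Binomial(n, 0.5). The exact probability of an absolute difference in shares of at least the stated size is:

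| n per arm | 15 points or more | 20 points or more |
|---|---|---|
| 30 | 25% | 16% |
| 40 | 22% | 9% |
| 60 | 12% | 4% |
| 100 | 4% | under 1% |

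With a 30:70 split of types, the 20-point figures are 12%, 7%, 2% and under 1%.

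**2. What a 20-point imbalance does to one trial.** Take n = 40, a split of 24 against 16, and a between-type difference d = 0.8 within-type SD.

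- Shift in the arm difference: 0.20 × 0.8 = 0.16 SD.
- Variance within an arm that an unadjusted test sees: 1 + 0.8² × 0.6 × 0.4 = 1.154.
- Standard error that the test uses: √(2 × 1.154/40) = 0.240. Rejection threshold: 1.96 × 0.240 = 0.471.
- Sampling SD of the difference once the mix is fixed: √(2/40) = 0.224.
- Upper tail: P(Z > (0.471 − 0.16)/0.224) = P(Z > 1.39) ≈ 0.082.
- Lower tail: P(Z < (−0.471 − 0.16)/0.224) = P(Z < −2.82) ≈ 0.002.
- Total: about 8%.

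A simulation with 30,000 runs gives 7.8% for the Mann-Whitney test and 7.9% for the t-test. At 15 points (23 against 17) it gives about 6%.

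**3. The error averaged over all allocations.** The same simulation, with the operation mix left to chance, gives about 5% for both tests. Well-balanced draws offset the unlucky ones. With an exact 20:20 split the unadjusted variance is 1 + 0.8²/4 = 1.16, the effective cut-off is 1.96 × √1.16 = 2.11, and the error is about 3.5%.

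**4. What adjustment would gain.** With two equal types, the between-type variance is d²/4, and its share of the total is (d²/4)/(1 + d²/4).

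- d = 0.5: 0.0625/1.0625 = 5.9%, worth 1/(1 − 0.059) − 1 ≈ 6% more patients.
- d = 1.0: 0.25/1.25 = 20%, worth 1/(1 − 0.20) − 1 = 25% more patients.

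This gain does not depend on any imbalance occurring. It is a share of the unadjusted variance. Once the preoperative value is also in the model, the added gain could differ.

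**The case against.** The strongest reply is that randomisation already deals with this. The P value allows for chance imbalance in every covariate, recorded or not, and step 3 confirms an overall error of 5%. That stands. A reader might infer that the arm comparison is biased, or that false positives are inflated in general. The documents support neither. The 8% applies only to a trial that has drawn a 20-point imbalance, and under the same assumptions about 9% of trials differ by that much or more. A calculation that fixes the outcome SD at 1 and ignores the between-type variance would give 11%, but the unadjusted test carries that variance, so 11% is too high.

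A reader might also infer that an imbalance could never be corrected. That goes too far. Duration of surgery, blood loss and transfusion are recorded and would show a gross difference. They remain imperfect substitutes: they arise after randomisation, and only the levobupivacaine arm receives a combined spinal-epidural, so their independence of arm is not guaranteed. Preoperative IL-6, CRP, fibrinogen and blood counts reflect inflammation before the operation, not the operation to come. Operation type itself should be recoverable from theatre records.

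Nor can one say that operation type is left out of the POCD analysis. The logistic regression's factors are unspecified, so the supportable wording is that operation type is not named.

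Finally, the title and the exclusion of multiple trauma narrow the population, and the documents do not describe the case mix. If one operation dominates, the concern shrinks. With about 100 per arm a large imbalance is unlikely, although the precision argument remains.

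**Conclusion.** The point holds as one of precision and interpretability. Fracture site and operation type are not named in the eligibility list, the recorded items, the allocation or the SAP, and the between-arm comparison of inflammatory markers has no adjustment. It is not a finding of systematic bias or of an inflated overall error rate.

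The size depends on quantities that the documents do not give: 40 per arm, two equally common types, and 0.5-1.0 SD between types. On those assumptions, imbalance is common enough to deserve a line in the baseline table, its effect on the error of one trial is modest, and the efficiency gain from adjustment is equivalent to 6-25% more patients. Adjustment is a cheap improvement that should be made.

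**What to change.** Take fracture site and planned operation class (for example replacement, nail, plate or screw) from theatre records for every randomised patient, and report both by arm. Alongside the Mann-Whitney test, fit a regression with operation class as a covariate, for example ANCOVA on log IL-6 and log CRP with the preoperative value included. Name operation class as a factor in the POCD logistic regression. Label these analyses post hoc if outcome data have been seen.

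Both documents are written in the past tense, so stratified allocation and new inclusion wording come too late for this trial, and the choice of stratification factor is in any case debatable.

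The cost is two data fields, one extra term per model (more than one parameter if operation class has more than two levels) and some retrospective record review. No patient needs an additional procedure.
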